[Part 2 of 2 of the document. The other parts are not shown.]

The ECGs to be used in the analyses will be selected by predetermined timepoints as defined in [Appendix 6](#) and will be read centrally by ERT (eResearch Technology Inc., Philadelphia, PA). The following principles will be followed in ERT's core laboratory:

- ECG analysts are blinded to the subject, visit, and treatment allocation.
- Baseline and on-treatment ECGs for a particular subject will be over-read on the same lead and will be analyzed by the same reader.

The primary analysis lead is lead II. If lead II is not analyzable, then the primary lead of analysis will be changed to another lead for the entire subject data set.

The 12-lead ECGs will be extracted in up to 10 replicates at the predefined timepoints and subjects will be inactive and in a supine position for at least 10 minutes prior to and 5 minutes after each nominal time.

7.2.1.1. *TQT Plus Extraction Technique*

Ten 14-second digital 12-lead ECG tracings will be extracted from the continuous Holter (or Mortara Surveyor) recordings using the 'TQT Plus method', a computer-assisted and statistical process utilized by ERT. The method enables extraction of ECGs with the lowest HR variability and noise within the protocol-specified extraction time window (eg, the HR and QT changes from beat-to-beat in the range of <10%). At each protocol-specified timepoint, 10 ECG replicates will be extracted from a 5-minute "ECG window" (typically,

the last 5 minutes of the 15-minute period when the subject is maintained in a supine, quiet position).

7.2.1.2. Expert Precision QT Analysis

Expert precision QT analysis will be performed on all analyzable (non-artifact) beats in the 10 ECG replicates. Statistical quality control procedures are used to review and assess all beats and identify “high” and “low” confidence beats using several criteria, including:

- QT or QTc values exceeding or below certain thresholds (biologically unlikely).
- RR values exceeding or below certain thresholds (biologically unlikely).
- Rapid changes in QT, QTc, or RR from beat-to-beat.

Measurements of all primary ECG parameters (QT, QTc, RR) in all recorded beats of all replicates that are deemed “high confidence” will be performed using COMPAS software. All low-confidence beats will be reviewed manually and adjudicated using pass-fail criteria. The final QC assessment will be performed by a cardiologist. The beats found acceptable by manual review will be included in the analysis. The median QT, QTc, and RR values from each extracted replicate will be calculated, and then the mean of all available medians from a nominal timepoint will be used as the subject’s reportable value at that timepoint.

Categorical T-wave morphology analysis and the measurement of PR and QRS interval of the ECG (QRS) intervals will be performed manually in 3 of the 10 ECG replicates at each timepoint. Each fiducial point (onset of P-wave, onset of Q-wave, offset of S-wave, and offset of T-wave) will be electronically marked.

For T-wave morphology and U-wave presence, treatment-emergent changes will be assessed (ie, changes not present at baseline). For each category of T-wave morphology and U-waves, the category will be deemed as present if observed in any replicate at the timepoint. For baseline, the category will be deemed as present if observed in any replicate from all timepoints that constitute baseline.

7.2.2. Safety 12-lead Electrocardiogram

Resting 12-lead ECGs will be recorded after the subject has been supine and at rest for at least 5 minutes at the times indicated in the Schedule of Assessments in [Appendix 6](#). Single 12-lead ECGs will be repeated twice, and an average taken of the 3 readings, if either of the following criteria applies:

- QT interval corrected for HR using Fridericia’s method (QTcF) is >500 ms
- QTcF change from the baseline (predose) is >60 ms.

Additional 12-lead ECGs may be performed at other times if judged to be clinically appropriate or if the ongoing review of the data suggests a more detailed assessment of ECGs is required. The investigator (or designee) will perform a clinical assessment of each 12-lead ECG.

7.2.3. Cardiac Telemetry Monitoring

Subjects will be monitored via cardiac telemetry from approximately 1 hour prior to dose administration and until approximately 12 hours postdose on Days 1, 2, 3, and 7 (up-titration days; as described in [Appendix 6](#)). Based on the emerging safety data from the study, the duration of the telemetry may be extended if necessary.

The start and stop date and time of the telemetry monitoring will be recorded in the eCRFs. Clinically significant abnormalities noted from telemetry monitoring will be confirmed by 12-lead ECG if necessary, then after confirming, the abnormalities will be reported as AEs in the eCRF.

7.3. Pharmacokinetic Assessments

7.3.1. Pharmacokinetic Blood Sample Collection and Processing

Blood samples (approximately 1 × 3 mL for CBP-307 and moxifloxacin assays) will be collected by venipuncture or cannulation at the times indicated in the Schedule of Assessments in [Appendix 6](#). Procedures for collection, processing, and shipping of PK blood samples will be detailed in a separate document.

7.3.2. Analytical Methodology

Plasma concentrations of CBP-307 and moxifloxacin will be determined using a validated analytical procedure. Specifics of the analytical method will be provided in a separate document.

7.4. Safety and Tolerability Assessments

7.4.1. Adverse Events

Adverse event definitions, assignment of severity and causality, and procedures for reporting SAEs are detailed in [Appendix 1](#).

The condition of each subject will be monitored from the time of signing the ICF until the follow-up visit. Subjects will be observed for any signs or symptoms and asked about their condition by open questioning, such as “How have you been feeling since you were last asked?”, at least once each day while resident at the study site and each study visit. Subjects will also be encouraged to spontaneously report AEs occurring at any other time during the study.

All nonserious AEs, whether reported by the subject voluntarily or upon questioning, or noted on physical examination, will be recorded from initiation of placebo administration to all subjects (Day -1) until study completion. If AEs that occur in the screening prior to placebo administration to all subjects (Day -1) are considered to be related to the study procedure, they should be also collected. Serious AEs will be recorded from the time the subject signs the ICF until study completion. The nature, time of onset, duration, and severity will be documented, together with an investigator’s (or designee’s) opinion of the relationship to study treatment.

Adverse events recorded during the course of the study will be followed up, where possible, to resolution or until the unresolved AEs are judged by the investigator (or designee) to have stabilized. This will be completed at the investigator's (or designee's) discretion.

7.4.2. Clinical Laboratory Evaluations

Blood and urine samples will be collected for clinical laboratory evaluations at the times indicated in the Schedule of Assessments in [Appendix 6](#). Clinical laboratory evaluations are listed in [Appendix 2](#).

A serum qualitative pregnancy or urine test (females only) and follicle-stimulating hormone test (postmenopausal females only) will be performed at the timepoints specified in [Appendix 6](#). A positive urine pregnancy test will be confirmed with a serum pregnancy test. All pregnancies should be reported as specified in [Appendix 1](#).

Additional clinical laboratory evaluations will be performed at other times if judged to be clinically appropriate or if the ongoing review of the data suggests a more detailed assessment of clinical laboratory safety evaluations is required. At the discretion of the investigator, clinically significant clinical laboratory assessments may be confirmed by repeat sampling. If the clinical significance is confirmed, subjects will be excluded from participation or, if already included, will be followed until normalization of the test result or for as long as the investigator considers necessary.

Subjects will be asked to provide urine samples for drugs of abuse screen and cotinine test, and will undergo an alcohol breath test at the times indicated in the Schedule of Assessments in [Appendix 6](#). For all female subjects, a pregnancy test will be performed at the times indicated in the Schedule of Assessments in [Appendix 6](#).

An investigator (or designee) will perform a clinical assessment of all clinical laboratory data.

7.4.3. Vital Signs

Supine blood pressure, supine pulse rate, respiratory rate, and tympanic temperature will be assessed at the times indicated in the Schedule of Assessments in [Appendix 6](#). Vital signs may also be performed at other times if judged to be clinically appropriate or if the ongoing review of the data suggests a more detailed assessment of vital signs is required.

All measurements will be performed singly. For all subjects, the screening, check-in, or baseline blood pressure, pulse rate, and respiratory rate may be repeated after 5 to 10 minutes if the initial reading is believed to be atypical for the subject.

Subjects must be supine for at least 5 minutes before blood pressure and pulse rate measurements.

7.4.4. Physical Examination

A full physical examination will be performed at the timepoints specified in the Schedule of Assessments in [Appendix 6](#). Physical examinations include general appearance, head, eyes,

ears, nose, and throat, neck (including thyroid and nodes), cardiovascular, respiratory, gastrointestinal, renal, neurological, musculoskeletal, skin, and others.

Height, weight, and body mass index will be assessed at screening.

8. SAMPLE SIZE AND DATA ANALYSIS

8.1. Determination of Sample Size

Approximately 64 healthy subjects (at least 30% for each sex) will be randomized into 2 groups (Group 1 and 2) with 32 subjects in each. Group 2 consists of 2 sub-groups (Group 2A and 2B) and each sub-group will be randomized with 16 subjects.

Sample Size for Primary Analysis:

A sample size of 28 evaluable subjects per treatment group will provide more than 94.4% power to exclude that CBP-307 causes more than 10-msec QTc effect at clinically relevant plasma levels, as shown by the upper bound of the 2-sided 90% confidence interval (CI) of the model-predicted QT effect ($\Delta\Delta\text{QTcF}$) at the observed geometric mean C_{max} of CBP-307 in the study. This power is estimated approximately using a 2-sample t-test. The calculation assumes a 1-sided 5% significance level, an underlying effect of CBP-307 of 3 msec and a standard deviation (SD) of the ΔQTcF of 8 msec for both CBP-307 and placebo treatment groups. Note that this calculation is conservative, since it does not take into account any gain in precision due to the use of all data of each subject with the help of a linear mixed-effects model. The concentration-QTc analysis method is supported by Darpo et al 2015³ and Ferber et al, 2015,⁴ and consistent with the experiences from 25 recent TQT studies.

Sample Size Considerations for Assay Sensitivity:

To demonstrate assay sensitivity with concentration-QTc analysis, it has to be shown that the $\Delta\Delta\text{QTcF}$ of a single dose of 400 mg moxifloxacin exceeds 5 msec (ie, the lower bound of the 2-sided 90% CI of the predicted QTc effect [$\Delta\Delta\text{QTcF}$] should exceed 5 msec). In a similarly designed, recent crossover study with 24 healthy subjects (on-file data, ERT), the standard error (SE) for the prediction of the QT effect of moxifloxacin based on the exposure-response analysis was 1.24 msec. The within-subject SD of ΔQTcF in the referred study was 5.4 msec based on the by-timepoint analysis. If the effect of moxifloxacin is assumed to be 10 msec, the SE of 1.24 msec corresponds to an effect size of $(10-5)/(1.24 \times \sqrt{24}) = 0.82$, where the effect size is the effect assumed under the alternative hypothesis divided by the SD of the test variable. This value should be compared to the effect size of 0.64 required to guarantee a power of at least 95% in a paired t-test situation with a sample size of 28 evaluable subjects. In other words, based on this calculation, a power of at least 95% will be obtained as long as the variability of the ΔQTcF , as measured by its within-subject SD from the by-timepoint analysis, does not exceed 6.9 msec (ie, 128% [= 0.82/0.64] of the 5.4 msec observed in the referred study assuming the ratio of effective sizes is consistent with inverse ratio of within-subject SD). The number also agrees with recent recommendations of the FDA, which propose at least 20 subjects.⁵

8.2. Analysis Populations

8.2.1. Cardiodynamic Population

The QT/QTc population will include all subjects in the safety population with measurements at baseline as well as on-treatment with at least 1 postdose timepoint with a valid Δ QTcF value. The QT/QTc population will be used for the by-timepoint and categorical analyses of the cardiodynamic ECG parameters.

The PK/QTc population will include all subjects who are in both the QT/QTc and PK populations with at least 1 pair of postdose PK and Δ QTcF data from the same timepoint as well as subjects in the QT/QTc population who received placebo. The PK/QTc population will be used for the concentration-QTc analysis and assay sensitivity. PK/QTc population will be defined for CBP-307, and for moxifloxacin.

The as-treated principle will be applied to all analysis populations mentioned below.

8.2.2. Pharmacokinetic Population

The PK population will include all subjects who received at least 1 dose of investigational product and have evaluable PK data of any of the analytes (CBP-307 and moxifloxacin). A subject will be excluded from the PK summary statistics and statistical analysis if the subject has an AE of vomiting that occurs at or before 2 times median time to maximum concentration.

8.2.3. Safety Population

The safety population will include all subjects who received at least 1 dose of investigational product drug (therapeutic and supratherapeutic doses of CBP-307, moxifloxacin, or placebo).

8.3. Cardiodynamic ECG Analyses

Baseline for Cardiodynamic ECG Assessments

Baseline for the assessment of the ECG effect of CBP-307 (CBP-307 in Group 1 versus placebo in Groups 2A and 2B) will be time-matched values on Day -1.

For assay sensitivity in Groups 2A and 2B, the following baselines will be used:

- Group 2A: For moxifloxacin administered on Day 1, baseline will be Day 16, on which subjects are administered placebo. For placebo-correction in this group, placebo values will be derived from Day 15 on which subjects are administered placebo, and baseline will be obtained on Day -1.
- Group 2B: For moxifloxacin administered on Day 16, baseline will be Day 1, on which subjects are administered placebo. For the placebo-correction in this group, Day -1 values will be used as placebo (no treatment) and baseline will be obtained on Day 15.

Concentration-QTc Analysis (Primary Analysis)

The relationship between CBP-307 plasma concentrations and change-from-baseline QTcF ($\Delta QTcF$) will be quantified using a linear mixed-effects modeling approach with $\Delta QTcF$ as the dependent variable, time-matched concentrations of CBP-307 as the exploratory variate (0 for placebo), treatment (active=1 or placebo=0), and time (ie, postbaseline timepoints on Days 1, 6, and 15 categorical) as fixed effects, and a random intercept and slope per subject.⁶

The degrees of freedom estimates will be determined by the Kenward-Roger method. From the model, the slope (ie, the regression parameter for the CBP-307 concentration) and the treatment effect-specific intercept will be estimated together with 2-sided 90% CI. The estimates for the time effect will be reported with degrees of freedom and SE.

For the assessment of the ECG effect of CBP-307 versus placebo, the time term incorporated into the models (both by-time point analysis and concentration-QTc analysis [or assay sensitivity]) includes the single predose timepoint and all postdose timepoints on Days 1, 6, and 15, and Days 1 and 16 for active versus placebo and moxifloxacin versus placebo, respectively. All times are relative to the time of dosing on that day which is considered the first dose for the assay sensitivity analysis. For the analysis of CBP-307 versus placebo, the first dose of study treatment is on Day 1.

The geometric mean of the individual C_{max} values for CBP-307 concentrations for subjects in the active drug groups on each of Days 6 and 15 will be determined, respectively. The predicted effect and its 2-sided 90% CI for placebo-corrected change-from-baseline QTcF ($\Delta\Delta QTcF$) (ie, slope estimate \times concentration + treatment effect-specific intercept) at this geometric mean C_{max} will be obtained.

To evaluate the adequacy of model fit with respect to the assumption of linearity, the observed $\Delta QTcF$ values adjusted by population time effect estimated from the model will be used. These individual placebo-adjusted $\Delta QTcF_{i,k}$ ($\Delta\Delta QTcF_{i,k}$) values equal the observed individual $\Delta QTcF_{i,k}$ for subject i administered with active drug or placebo at timepoint k minus the estimated population mean placebo effect at timepoint k (ie, time effect). A decile plot, ie, plot of the deciles of observed concentrations and the mean placebo-adjusted $\Delta QTcF$ ($\Delta\Delta QTcF$) and 90% CI at the median concentration within each decile will be given. The regression line presenting the model-predicted $\Delta\Delta QTcF$ ⁷ will be added to evaluate the fit of a linear model and visualize the concentration-response relationship. The placebo-adjusted $\Delta QTcF_{i,j}$ equals the individual $\Delta QTcF_{i,j}$ for subject i administered with CBP-307 at timepoint j minus the estimation of time at timepoint j (ie, time effect). Additional exploratory analyses (via graphical displays and/or model fitting) will include accounting for a delayed effect (hysteresis) and the justification for the choice of PD model (linear versus nonlinear) as follows.

Criteria for Negative QT Assessment

If the upper bound of the 2-sided 90% CI of the predicted QTc effect of $\Delta\Delta QTcF$ at the observed geometric mean C_{max} on Days 6 and 15 as well as clinically relevant plasma levels is below 10 msec (ie, the upper bound of the 2-sided 90% CI at the geometric mean C_{max}

<10 msec), it can be concluded that CBP-307 does not cause clinically concerning QT prolongation within the observed plasma concentration ranges.

Investigation of Hysteresis

Hysteresis will be assessed based on joint graphical displays of the least squares (LS) mean $\Delta\Delta QTcF$ for each postbaseline timepoint and the mean concentration of CBP-307 at the same timepoints. In addition, hysteresis plots will be given for LS mean $\Delta\Delta QTcF$ and the mean concentrations. If a QT effect ($\Delta\Delta QTcF$) >10 msec cannot be excluded from the by-timepoint analysis in the active dose groups on Days 6 and 15; and the mean peak $\Delta\Delta QTcF$ effect is observed at the same timepoint in the by-timepoint analysis in the active dose groups on Days 6 and 15; and if the difference (delay) between the time to reach the peak QTc effect ($\Delta\Delta QTcF$) and peak plasma concentration (t_{max}) in the plot ($\Delta\Delta QTcF$ versus CBP-307) of more than 1 hour is observed in a consistent way for the active dose groups on Days 6 and 15, other concentration-QTc models, such as a model with an effect compartment, may be explored. With the provision stated above, hysteresis will be assumed if this curve shows a counterclockwise loop. A significant treatment effect-specific intercept may also be indicative of hysteresis or model misspecification, if it cannot be explained by a nonlinear relationship.

Appropriateness of a Linear Model

To assess the appropriateness of a linear model, normal quantile-quantile plots for the standardized residuals and the random effects, scatter plots of standardized residuals versus concentration and versus fitted values, and box plots of standardized residuals versus nominal time and versus active treatment will be produced. The scatter plot of standardized residuals versus concentration by locally estimated scatterplot smoothing (LOESS) fitting (ie, locally weighted scatterplot smoothing⁸ lines) also will be produced with an optimal smoothing parameter selected by the Akaike information criterion with a correction.⁹ In addition, a scatter plot of observed concentration and $\Delta QTcF$ with a LOESS smooth line with 90% CI and a linear regression line will also be provided to check the assumption of a linear concentration-QTc relationship. If there is an indication that a linear model is inappropriate, additional models may be fitted, such as an E-max model. The concentration-QTc analysis will then be repeated for the model found to best accommodate the nonlinearity detected.

Assay Sensitivity

Assay sensitivity will be demonstrated by similar concentration-QTc analysis of moxifloxacin data. If the slope of the concentration-QTc (change-from-baseline QTcF) for moxifloxacin is statistically significant at 10% level for 2-sided test and the lower bound of the 2-sided 90% CI of the predicted effect is above 5 msec at the observed geometric mean C_{max} of the 400-mg dose, assay sensitivity will be deemed to have been demonstrated.

By-Timepoint Analysis

The analysis for QTcF for CBP-307 versus placebo will be based on a linear mixed-effects model with change-from-baseline QTcF ($\Delta QTcF$) as the dependent variable, time (ie, postbaseline timepoints on Days 1, 6, and 15: categorical), treatment (therapeutic dose of CBP-307 and supratherapeutic dose of CBP-307 on Day 15, and corresponding placebo), and

time-by-treatment interaction as fixed effects. An unstructured covariance matrix will be specified for the repeated measures at postdose timepoints within subjects. If the model with unstructured covariance matrix fails to converge, other covariance matrices such as compound symmetry and autoregressive will be considered. From this analysis, the LS mean, SE, and 2-sided 90% CIs will be calculated for the contrast “CBP-307 versus placebo” for each day of Days 1, 6, and 15 at each postbaseline timepoint on Days 1, 6, and Day 15, respectively.

The by-time point analysis for QTcF will be also performed for moxifloxacin versus placebo at postbaseline timepoints on Day 1 and Day 16. A linear mixed-effects model will be used with Δ QTcF as the dependent variable and time (ie, postbaseline timepoints on Days 1 and 16: categorical), treatment (moxifloxacin and placebo), sequence (placebo/moxifloxacin or moxifloxacin/placebo), and time-by-treatment interaction as fixed effects. An unstructured covariance matrix will be specified for the repeated measures at postbaseline timepoints for subject within visit. The model will also include a subject-specific random effect. If the model with an unstructured covariance matrix fails to converge, other covariance matrices, such as compound symmetry or autoregressive, will be considered. From this analysis, the LS mean, SE, and 2-sided 90% CIs will be calculated for the contrast “moxifloxacin versus placebo” at each postbaseline timepoint, respectively.

For HR, PR, and QRS intervals, the analysis will be based on the change-from-baseline postdose (Δ HR, Δ PR, Δ QRS). The same (by-timepoint analysis) model will be used as described for QTcF. The LS mean, SE, and 90% CI from the statistical modeling for both change-from-baseline and placebo-corrected change-from-baseline values will be listed in the tables and graphically displayed.

Categorical Analyses

The analysis results for categorical outliers, T-wave morphology, and U-wave presence will be summarized in frequency tables with counts (percentages) for both the number of subjects and the number of timepoints. For categorical outliers, the number (percentage) of subjects as well as timepoints who had increases in absolute QTcF values >450 and ≤ 480 msec, >480 and ≤ 500 msec, or >500 msec, and changes from predose baseline of >30 and ≤ 60 msec, or >60 msec; increase in PR from predose baseline $>25\%$ to a PR > 200 msec; increase in QRS from predose baseline $>25\%$ to a QRS >120 msec; decrease in HR from predose baseline $>25\%$ to an HR <50 bpm; and increase in HR from predose baseline $>25\%$ to an HR >100 bpm will be determined. For T-wave morphology and U-wave presence, the analyses will be focused on change from baseline (ie, treatment-emergent changes).

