3. **Screening and Check-in on Day -2:** Tympanic temperature, respiratory rate, and supine pulse rate and blood pressure. **Other days (except for Days 17, 18, and 19):** Prior to and 2 hours after dosing, supine vital signs (tympanic temperature, pulse rate, respiratory rate, and blood pressure). **Days 17 and 18:** Tympanic temperature, respiratory rate, and supine pulse rate and blood pressure at approximately the same time each day. **Discharge (Day 19):** Prior to discharge, supine vital signs (tympanic temperature, pulse rate, respiratory rate, and blood pressure). **End of Study/Follow-up Visit (Day 29±2 days):** Tympanic temperature, respiratory rate, and supine pulse rate and blood pressure.

4. 12-lead safety ECG will be recorded in triplicates before dosing and in singles 2 hours postdose on all study days (except for Days 17 and 18) and before discharge on Day 19. Postdose safety will be interpreted on-site by the investigator and may be repeated to confirm/refute clinically abnormal findings.
5. Continuous cardiodynamic monitoring (Holter) will be performed for 25 hours on Day -1 (baseline), 1, 6, 15, and 16. The recording will be started at least 1 hour before dosing and at the corresponding clock time on Day -1. Replicate 12-lead ECGs will be extracted from the continuous recording prior to dosing (-30 minutes) and 0.5, 1, 2, 3, 4, 6, 8, 12, and 24 hours postdose on each day. At timepoints for ECG extractions, subjects will be supinely resting in an undisturbed environment. The ECG effects of CBP-307 will be tested on data from Day -1 (baseline for both groups), Day 6 (therapeutic concentrations versus placebo), and Day 15 (supratherapeutic concentrations versus placebo). Assay sensitivity with moxifloxacin will be tested on data from Days -1, 1, 15, and 16.
6. Serum pregnancy test will be performed at screening and urine pregnancy tests will be performed on Day -2 and at the follow-up visit (Day 29±2 days). A positive urine pregnancy test will be confirmed with a serum pregnancy test.
7. Pharmacokinetic samplings will be performed prior to dosing and 0.5, 1, 2, 3, 4, 6, 8, 12, and 24 hours after dosing on each PK sampling day (Days 1, 6, 15, and 16). Additional PK samples will be collected at 72 and 96 hours following dosing on Day 15.

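### The moxifloxacin baselines in Section 8.3 pair days about two weeks apart, so QTc drift enters the two sub-groups doubled and with opposite sign, and the placebo changes fall on days outside the models' stated time term

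*Protocol*

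**What the plan says.** Section 8.3 of the protocol, under the baseline heading, sets four changes for assay sensitivity.

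- Group 2A, moxifloxacin: "For moxifloxacin administered on Day 1, baseline will be Day 16, on which subjects are administered placebo".
- Group 2A, placebo: "placebo values will be derived from Day 15 on which subjects are administered placebo, and baseline will be obtained on Day -1".
- Group 2B, moxifloxacin: "For moxifloxacin administered on Day 16, baseline will be Day 1, on which subjects are administered placebo".
- Group 2B, placebo: "Day -1 values will be used as placebo (no treatment) and baseline will be obtained on Day 15".

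The same section then describes the time term as covering "Days 1 and 16 for active versus placebo and moxifloxacin versus placebo, respectively", and adds: "All times are relative to the time of dosing on that day which is considered the first dose for the assay sensitivity analysis". The by-timepoint model for moxifloxacin has "time (ie, postbaseline timepoints on Days 1 and 16: categorical), treatment (moxifloxacin and placebo), sequence (placebo/moxifloxacin or moxifloxacin/placebo"), plus a time-by-treatment interaction and a subject random effect. No day or period term is listed. The concentration-QTc model for moxifloxacin is described only as similar to the primary one. Footnote 5 of Appendix 6 says: "Assay sensitivity with moxifloxacin will be tested on data from Days -1, 1, 15, and 16".

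**The concern.** Each change subtracts a recording made 15 days away (Day 1 and Day 16; Day -1 and Day 15, there being no Day 0). Two of the four changes, moxifloxacin in 2A and placebo in 2B, use a baseline recorded after the day it serves. A slow shift in QTc over the confinement therefore does not cancel within a subject.

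The model text describes something different: a two-period crossover with Days 1 and 16 as the treatment days. That agrees with Table 3, but under the baseline bullets no placebo change exists on either day.

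Assay sensitivity requires the lower 90% bound of the moxifloxacin effect to exceed 5 msec, so extra width or bias in this contrast bears directly on whether the criterion is met.

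**Working it through.** **Inputs.** From Section 8.1: assumed moxifloxacin effect 10 msec, threshold 5 msec, reference SE 1.24 msec with 24 subjects, 28 evaluable subjects, 16 randomized to each of 2A and 2B. From Section 8.3: the day pairings and a 2-sided 90% interval (1-sided 5%). Assumed, because the documents give no figure: a common drift D from Days -1/1 to Days 15/16, taken from 0 to 5 msec.

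**The plan's own figure.** SD of the test variable = 1.24 × √24 = 6.07 msec. Effect size = (10 − 5)/6.07 = 0.82. A paired t-test with n = 28, 1-sided 5%, has 95.1% power at effect size 0.64, so the protocol's statement reproduces. At 0.82 the power is 99.5%.

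**Drift algebra.** Let M be the true effect and Y the time-matched QTcF on each day.

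- 2A: (Y1 − Y16) − (Y15 − Y−1) = M − 2D.
- 2B: (Y16 − Y1) − (Y−1 − Y15) = M + 2D.

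This is exact for a linear drift of D over the 15 days and for a step of D. With M = 10 and D = 3 the sub-groups show 4 and 16 msec. In 2A the moxifloxacin change carries −D and the placebo change +D; in 2B the signs are reversed. The drift averages to zero within each sequence, so the sequence main effect takes up none of it.

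**Estimability.** The four cells are 2A moxifloxacin (Day 1), 2A placebo (Day 15), 2B moxifloxacin (Day 16) and 2B placebo (Day -1).

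- Time levels specific to each day: every day holds one treatment in one sequence, and a rank check shows that treatment is not estimable.
- Time as hours after dosing: treatment is estimable, but no listed term absorbs D.
- Written pairing, hours after dosing, plus an early/late period term: treatment is estimable and D is removed exactly.
- Adjacent-day pairing with day-specific levels: treatment is estimable.

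**Power with equal numbers.** Simulated one-sample t-test on the per-subject contrast, 14 per sequence, SD 6.07, M = 10, shift fixed at −2D or +2D by sequence, no period term. The mean is unbiased; only the estimated SE grows.

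| D (msec) | Power |
|---|---|
| 0 | 99.5% |
| 2 | 98.7% |
| 3 | 97% |
| 4 | 93% |
| 5 | 84% |

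Power falls below 95% at D of about 3.6 msec.

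**Unequal numbers.** Bias = 2D(nB − nA)/(nA + nB). At D = 3:

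- 16 in 2A, 12 in 2B: 2 × 3 × (12 − 16)/28 = −0.86 msec, power about 88%.
- 12 in 2A, 16 in 2B: +0.86 msec, power above 99%.

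**Adjacent-day pairing.** 2A: (Y1 − Y−1) − (Y16 − Y15); 2B: (Y16 − Y15) − (Y1 − Y−1). A step between the two ends of the stay, or a linear drift, contributes zero in both.

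**The case against.** The strongest reply is that the design already protects the pooled estimate. The sequences are randomized 16 and 16, the drift has opposite sign in the two, and with equal evaluable numbers it cancels. Subjects are confined on a standardized diet without caffeine, ECGs are taken supine, and each subject is read on one lead by one reader, so a large common drift is not to be expected. Section 4.4 allows replacement of subjects withdrawn for reasons unrelated to treatment, which limits imbalance. Assay sensitivity is a secondary objective, and the CBP-307 analysis uses Day -1 baselines and is untouched. All of this stands, and it limits the size of the point.

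Three stronger readings are tempting and are not supported.

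- A reader might infer that drift generally biases the moxifloxacin effect. It does so only when the evaluable numbers differ, and the sign depends on which sub-group loses subjects.
- A reader might add (2D)² to the variance, obtain 91.5% power at D = 3 and 71% at D = 5, and conclude that 95% is lost at about 2.5 msec. That treats a shift fixed by sequence as random between subjects. Section 8.1 fixes the sequence sizes, so at equal numbers the sampling SD of the mean stays at 6.07/√28 = 1.15 msec.
- A reader might infer that the contrast cannot be estimated at all. That holds only with day-specific time levels. The sentence making times relative to dosing permits hours after dosing, under which the model can be fitted.

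It can also be said that a period term may be left to the SAP, which is not shown. But the protocol itself fixes the pairing and names the days of the time term, and those two statements do not agree.

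**Conclusion.** The point holds at moderate weight and should be fixed. The written pairing carries drift at −2D and +2D, no stated term removes it, and the placebo changes lie on days that the time term does not name. The mismatch between bullets and model needs correcting whatever the drift.

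With equal numbers the consequence is a wider interval, and the stated 95% power survives up to D of about 3.6 msec. With unequal numbers there is bias: a loss concentrated in 2B under upward drift makes assay sensitivity harder to show, and a loss concentrated in 2A favours claiming it.

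These figures rest on an assumed common drift, the reference study's SD, and the protocol's own paired t-test approximation rather than the full concentration-QTc model.

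**What to change.** Reword the two baseline bullets in Section 8.3 to use adjacent-day, time-matched baselines:

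- Group 2A: moxifloxacin = Day 1 minus Day -1; placebo = Day 16 minus Day 15.
- Group 2B: placebo = Day 1 minus Day -1; moxifloxacin = Day 16 minus Day 15.

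Both treatments then have changes on Days 1 and 16, and the stated day-by-time term acts as the period effect. That term also absorbs any common Day -1 to Day 1 or Day 15 to Day 16 change that the pairing itself does not cancel.

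If the present pairing is kept, define time as hours after dosing, name Days -1 and 15 as sources of placebo values, and add a period term (Days -1 and 1 against Days 15 and 16) to both moxifloxacin models.

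In either case, reconcile the description of Day -1 as no treatment with Table 3, which lists a placebo capsule that day.

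The cost is a text change in the protocol and the matching SAP wording. The four recordings are already scheduled in Appendix 6, so no new ECGs or subjects are needed.
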